10.3 Historical Control Patient Participants

10.3.1 Screening and Enrollment

Controls will be matched 1:5 with enrolled patient participants based on clinic and primary care provider and identified through a review of medical records. Additionally, CRDS will be used to screen for historical controls at the UW Health Family Medicine Clinic in Belleville, and data will be delivered to the study team through REDCap. Controls will be identified and selected starting from the date 3 months prior to clinic activation and going back in time until the required number is reached. . The 3-month wash-out will avoid contaminating primary care teams with intervention activation events. Patients receiving palliative care, those unable to provide consent, and those who lacked insurance covering referral to University of Wisconsin specialty clinics will be excluded from the control population consistent with prospectively enrolled patient participants.

A waiver of informed consent and HIPAA authorization waiver has been obtained for data abstraction activities for historical controls. This aspect of the study meets the four criteria for a waiver of HIPAA authorization. First, the research involves no more than minimal risk to the historical controls as it consists of a chart review only. Second, the research could not practicably be carried out without the

waiver since a substantial proportion of the historical controls are likely to have died (~20% in our national cohort study were dead within one year). Third, the research could not practically be carried out without using Identifiable Private Information because we need to access their medical records, which contain the most accurate record of what care they received for their foot ulcer. Fourth, the waiver is unlikely to adversely affect the rights and welfare of the subjects due to the procedures we have in place to maintain the confidentiality of all participants, both historical and prospective.

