3.0	06/24/2024	
 1) Updated "[name]" with "[name]" (name and contact info) 2) Updated qualitative retention interview inclusion criteria 3) Updates and additions were made to the qualitative retention interview portion of the interview guide 	
 1) [name] has replaced [name] as research coordinator of the study. 2) We expanded our inclusion criteria and anticipated number of participants for the retention interviews so that we could include key informants from the clinic level, such as administrators. 3) We made some edits/additions after review of the first few retention interviews conducted with patient participants.
3.1	08/28/2024	Increased the number of healthcare worker (HCW) participants and patient participants for qualitative retention interviews by 1 each	A HCW that we'd like to interview was out on medical leave when we were recruiting; she has since returned to work and got back to us expressing interest in participating (and we have the funds to cover additional interviews). We are also increasing our maximum patient participants by one.
4.0	10/14/2024	Changed reimbursement method to Advarra, added patient information letter as a new retention strategy, added qualitative questions to see what patients thought about the new letter	UW policy is mandating switching to Advarra for study reimbursements as of 01/01/2025; initial qualitative interviews of patients suggested we should add a letter to serve as a reminder about the goals of the study and what to expect
5.0	02/06/2025	Updated ratio of active patients to historical controls & removed the date constraint for historical controls; removed [name]'s work phone number	
Per our statistician, with our final number of active patients, we need 135 historical controls for 80% power. We have exhausted our options within the date constraint initially included due to COVID. We think it's more important to be adequately powered and will include COVID as a limitation.
 
[name] will no longer have a dedicated UW number as of 2/28/25

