7.0 STUDY DESIGN

7.1 General Design

This is a phase II pilot of an integrated care model for treatment of diabetic foot ulcers in rural patient populations and includes adaptive recruitment and retention strategies. The protocol uses a pre-post serial cohort design, where the second and third clinics are activated six months after the first clinic and all clinics complete the trial simultaneously. This design allows: 1) use of refined recruitment and retention strategies when the final two clinics are activated, and 2) dispersion of activation efforts to facilitate completion by small research teams. Subject accrual will occur over 24 months. The design was modified so that clinics 2 and 3 could be activated simultaneously based on 1) our 100% recruitment of healthcare workers from clinic 1, which was greater than expected, and 2) our lower than expected patient recruitment from clinic 1. Having the third clinic activated for longer than initially planned should increase our likelihood of recruiting enough patients into the trial.

The study population will consist of 45 patient participants that develop diabetic foot ulcers during the enrollment period and receive care from participating rural providers (primary care providers (PCPs) at UW Health Belleville and diabetes or wound care providers at Sauk Prairie Healthcare) at rural clinics taking part in the study. Clinic schedulers, in addition to rural providers, will also be enrolled. Patient participants will be eligible only if their rural provider already consented and enrolled in the study. Patient participants will complete screening activities and their rural provider(s) and clinic scheduler will use the integrated care model to assist with care decisions (although rural providers will retain clinic discretion to deviate from the integrated care model to best serve the patient). Study activities include screening, chart reviews, and telephone assessments. Historical control data from up to 180 patients (1:5 active patient enrollment: historical control matching) will be obtained from medical records for comparison. Historical controls will be matched based on clinic and providers but no other factors due to the low overall volume of patients on any one provider's panel with diabetic foot ulcers.

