18.10 Appendix 10: Integrated Care Model Chart Review Variables

Patient characteristics	Sociodemographics	Age, sex, race, marital status, area deprivation index, insurance, clinic 1-3, primary care provider, all assessed at baseline
	Comorbidities	Charlson comorbidity index, hypertension, hyperlipidemia, coronary artery disease, stroke/TIA, peripheral vascular disease, end-stage renal disease, peripheral neuropathy, Charcot arthropathy, body mass index, smoking status, all assessed at baseline
	Medications	Use of anticoagulant, angiotensin reductase inhibitor, angiotensin II receptor blocker, all assessed at baseline and 3-month follow-up
	Lab values	Hemoglobin A1C, serum creatinine, both assessed at baseline and 3-month follow-up
	Ulcer characteristics	Date of diagnosis, Wagner severity ¹⁰⁴ grade at baseline and 3-month follow-up
Care processes	5 Vascular disease care processes	
 1) Baseline exam documents pedal pulse assessment 2) Baseline visit documents smoking status and cessation counseling within 3-months if indicated 3) Baseline visit documents statin use, and started within 3-months if indicated 4) ABI completed in 1 week for patients with decreased/absent pulses 5) Patients with ABIs ≤0.7 seen by vascular surgery within 2 weeks
	4 Infectious disease care processes	
 1) Baseline plain films for serial assessment of osteomyelitis 2) All exams document the presence/absence of findings suggestive of infection 3) Initial soft tissue infections treated with 2 weeks of broad spectrum antibiotics 4) Patients with concerns of, deep space abscess or osteomyelitis referred to a surgeon and/or infectious disease consultation in 2 weeks
	Other care processes	ABI results, referral to additional consultants (e.g., podiatry), whether vascular surgery and infectious disease consults were in-person or via telehealth, whether vascular surgery or infectious disease consults were never scheduled, canceled, or no-shows, all assessed at 3-month follow-up
	Ulcer status	Healed, ulcerated, major or minor amputation at 3 months, assessed by chart review for all patients & by patient report for those receiving integrated care
	Death	Patient died within the 3-month follow-up

18.11 Appendix 11: Phone Script for Recruitment of Participants for Qualitative Recruitment Interviews

Recruitment Telephone Script for Qualitative Recruitment Interviews

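### Historical controls have no earliest date, the COVID-related date limit was dropped to reach 135, and no analysis by calendar period is specified

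*Combined protocol and SAP*

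**What the plan says.** **Selection.** Section 10.3.1 starts three months before clinic activation and works backwards, "going back in time until the required number is reached". It gives no earliest date.

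**Why there is no earliest date.** The version 5.0 entry in the protocol history records that the team "removed the date constraint for historical controls". Its reason: "We have exhausted our options within the date constraint initially included due to COVID". On the consequence it says: "We think it's more important to be adequately powered and will include COVID as a limitation". This entry is cited for the rationale; it agrees with the current text of section 10.3.1.

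**Matching.** Section 7.1: "Historical controls will be matched based on clinic and providers but no other factors". Calendar time is not a matching factor.

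**Analysis.** Section 13.2 stratifies by clinic. It names a multivariable Poisson model for the dichotomous care-process endpoint and for amputation, and linear regression for the percentage endpoint. It lists no covariates and describes no analysis by calendar period and none that sets COVID-era controls apart.

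**Data.** Appendix 10 includes "Date of diagnosis, Wagner severity" among the ulcer characteristics, so the date needed is already abstracted.

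**The concern.** In a pre-post design the arm contrast contains whatever else changed between the two periods. Here the sponsor recognised one such change, set a date limit because of it, and removed the limit for sample size without putting an analysis in its place.

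The endpoint is exposed to period effects. Appendix 10 scores timed ankle-brachial testing, specialist visits within two weeks, baseline plain films and documentation of pulses, smoking and statin use. Section 13.2 counts telemedicine visits as completed. Clinic access, imaging, telemedicine and charting habits could all differ between a COVID-era or older control and a recent active patient.

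If usual care improved over time, or dipped during COVID among controls, the intervention looks better than it is. If usual care worsened towards the active period, a real benefit is hidden. Section 14.3 intends the pilot as preliminary efficacy evidence for a statewide trial, so an error either way would carry forward.

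**Working it through.** **1. The plan's own power figure.** Inputs from section 13.2: n = 27 active patients, M = 5 controls each, control probability p0 = 0.6, matched correlation φ = 0.3, odds ratio ψ = 0.26, alpha 0.05 (taken as two-sided). I used the Dupont matched-set method, writing q = 1 − p.

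- Control probability given an exposed or unexposed active patient: p0+ = [p1·p0 + φ√(p1·q1·p0·q0)]/p1 and p0− = [q1·p0 − φ√(p1·q1·p0·q0)]/q1.
- Solving ψ = p1(1 − p0+)/(q1·p0−) gives p1 = 0.375.
- Let t_m be the probability of m exposed members in a set. Then e_ψ = Σ m·t_m·ψ/(mψ + M − m + 1) and v_ψ = Σ m·t_m·ψ(M − m + 1)/(mψ + M − m + 1)².
- Power = Φ{[√n(e_1 − e_ψ) − 1.96√v_1]/√v_ψ} = 0.8071, against 0.80706 stated. It reproduces.

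**2. Cost of fewer controls, same inputs.**

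| Controls per active patient | 5 | 4 | 3 | 2 | 1 |
|---|---|---|---|---|---|
| Power | 0.807 | 0.779 | 0.732 | 0.647 | 0.464 |

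**3. Size of a period shift (assumptions, not document figures).** Assume active patients spread evenly over the 24-month accrual of section 7.1, the 0.25-year wash-out of section 10.3.1, and controls spread evenly over L years. The gap in mean diagnosis date is 1 + 0.25 + L/2.

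- L = 4: gap 3.25 years. Drift of 2 or 3 points per year gives 6.5 or 9.75 points.
- L = 1.5: gap 2.0 years, so 4 or 6 points. Section 16.3 expects 30 to 35 ulcers per clinic per year, so three clinics would yield 135 controls in 135/105 = 1.3 to 135/90 = 1.5 years.

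**4. False-positive rate with no true effect.** Test: z = (p̂a − p̂c)/√[p̄(1 − p̄)(1/27 + 1/135)], two-sided 0.05. I summed exact binomial probabilities over all outcomes, with control rate p and active rate p + shift. Matching is ignored. Control rates run from 20% (synopsis) to 60% (section 13.2).

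| Shift | p = 20% | p = 40% | p = 60% |
|---|---|---|---|
| 0 | 0.049 | 0.050 | 0.050 |
| 4 points | 0.086 | 0.070 | 0.063 |
| 6 points | 0.122 | 0.093 | 0.083 |
| 6.5 points | 0.133 | 0.100 | 0.090 |
| 9.75 points | 0.218 | 0.161 | 0.148 |

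In the other direction, a usual-care fall of 6.5 or 9.75 points would make a true 30-point gain (the synopsis effect) read on average as 30 − 6.5 = 23.5 or 30 − 9.75 = 20.25 points.

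**5. Would a linear date term solve it?** Variance inflation is 1 + B/W, with B = (27·135/162²)·gap² and W = (27·2²/12 + 135·L²/12)/162.

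- L = 1.5: 1 + 0.556/0.212 = 3.62, so the arm standard error is multiplied by 1.90.
- L = 4: 1 + 1.467/1.167 = 2.26, multiplier 1.50.
- L = 8: 1 + 3.828/4.5 = 1.85, multiplier 1.36.

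So the term can be fitted, but it need not remove a temporary dip. Assume a 15-point dip lasting 1.5 years among controls and no intervention effect. The adjusted bias is the unadjusted bias minus (pooled within-group slope × gap).

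- L = 4: unadjusted bias 15 × 1.5/4 = 5.6 points. Dip from 3 to 1.5 years before activation: slope 0, bias stays 5.6. Dip from 2 to 0.5 years before: slope −4.02 per year, bias 5.6 + 4.02 × 3.25 = 18.7.
- L = 3: unadjusted bias 15 × 1.5/3 = 7.5 points. Dip from 3 to 1.5 years before: slope 4.59 per year, bias 7.5 − 4.59 × 2.75 = −5.1.

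The linear term can leave the bias unchanged, enlarge it or reverse it.

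**The case against.** Several points on the other side are sound.

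- **Selection is not unbounded.** The most recent controls are taken first and selection stops at the required number. At the section 16.3 incidence the look-back would be about 1.5 years and the shift smaller. However, the version 5.0 entry says supply inside the earlier limit ran out, so that incidence may be optimistic.
- **A reader might infer that the section 13.2 models leave out calendar time.** The documents do not show this. The covariates are unlisted, so a date term is neither planned nor excluded. What can be said is that none is specified.
- **A reader might also infer that the bias favours the intervention.** That is not established. No trend in care processes is given, and the trends in section 5.1 (rising amputations and risk factors) would tend to work against the intervention on the secondary endpoint.
- **The numbers are illustrative.** Drift and look-back have no source, the test ignores matching, and it is not the planned Poisson model.
- **Date adjustment should not be the test of robustness.** Within a clinic, control and active dates do not overlap, so the model extrapolates. Step 5 shows how that can mislead.
- **This is a pilot that concedes COVID as a limitation**, with matching on clinic and provider.

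These points narrow the claim and rule out date adjustment as the remedy. They do not fill the gap: a limitation statement says bias may exist, while a restricted analysis shows how far the result depends on the added controls.

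**Conclusion.** The concern holds in limited form. The control pool has no earliest date, a known COVID safeguard was removed for power, and no period analysis is specified although diagnosis date is collected. A secular or COVID-era change could therefore mimic or mask an effect, and the plan gives no means of telling.

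The size is unknown. Under the assumed 4-year look-back and drift of 2 to 3 points a year, the false-positive rate would be 0.09 to 0.22 instead of 0.05, depending on drift and control rate. With the shorter look-back implied by section 16.3 it would be about 0.06 to 0.12. These ranges show that the issue merits an analysis; they do not estimate the bias in this trial. The documents do not support saying that the result will be falsely positive, or that the 1:5 primary analysis should be abandoned.

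**What to change.** Keep the 1:5 primary analysis. Before outcome data are analysed, add to section 13.2:

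1. One prespecified sensitivity analysis of the primary endpoint, using only controls eligible under the date limit in force before version 5.0. The current text does not give that window, but the sponsor holds it and should state it. To the same end, controls diagnosed in a stated COVID period could be excluded instead.
2. A descriptive report of care-process completion by diagnosis year among controls.

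Report the restricted estimate and interval beside the primary estimate, and qualify the conclusion if they differ materially. A model with a linear diagnosis-date term may be shown as exploratory only, with its reliance on extrapolation stated.

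**Cost:** protocol wording, one further model run and one table, with no new patients, charts or variables. The restricted analysis will have a wider interval: on the section 13.2 inputs, power is about 0.73 if three controls per active patient remain and 0.65 if two remain, against 0.81 at five. The number actually inside the earlier window is not given. Enrolment is complete and version 6.0 already arranges the statistician's dataset, so the wording should be settled now.

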10.3.2 Data Abstraction

Medical records will be reviewed, and similar data collected from prospectively enrolled patient participants will be extracted from historical control patient participants. This includes sociodemographic data, comorbidities, medications, lab values, and ulcer characteristics at baseline and at 3 months post-baseline. Amputation and death data will also be collected, if applicable. See Appendix for the full list of variables.

11.0 ADAPTIVE RECRUITMENT AND RETENTION PROCEDURES

11.1 Interview Procedures (Qualitative Data Collection)

11.1.1 Subject Identification and Recruitment

11.1.1.1 Recruitment Interviews

Up to 9 healthcare workers and 9 patient participants from each clinic will be identified to participate in recruitment interviews (n=18 total participants). We will purposively sample across roles (i.e., rural providers/schedulers), those who consented or declined participation in the integrated care model intervention, and oversample both healthcare workers and patient participants from under-represented minority populations.

A research coordinator not participating directly in recruitment efforts will reach out to patients by telephone and healthcare workers by telephone or email to assess their interest in scheduling an interview. Up to three attempts will be made to reach potential interviewees. If a call is not answered, the coordinator will leave a message inviting the participant to return the call. A scripted telephone invitation and template email to participate in the qualitative portion of this study is included in the Appendix. The method of contact will be determined based on the participant's preferred method of contact as noted when they filled out the Demographics CRF.

Identification and recruitment activities will take place within 3 months of each clinic being activated for the integrated care model intervention.

11.1.1.2 Retention Interviews

Up to ten healthcare workers and ten patient participants will be identified to participate in retention interviews (n=20 total participants). These individuals will be sampled to reflect their experiences across retention adaptations and clinics. In addition to healthcare workers enrolled in the quantitative portion, we will also recruit clinic administrators and staff who helped patient recruitment efforts and support clinic engagement with this study (e.g., help set-up meetings with clinicians, facilitate electronic health record access with the study coordinators, serve as ombudsmen to the larger healthcare system with respect to study activities). We anticipate significant overlap between people who agree to participate in the recruitment and retention interviews. In total, we will not enroll more than 36 people between these two efforts.

A research coordinator not participating directly in recruitment and retention efforts at that clinic will reach out to patients by telephone and healthcare workers by telephone or email to assess their

interest in scheduling an interview. Up to three attempts will be made to reach potential interviewees by phone. If a call is not answered, the coordinator will leave a message inviting the participant to return the call. A scripted telephone invitation and template email to participate in the qualitative portion of this study is included in the Appendix. The method of contact will be determined based on the participant's preferred method of contact as noted when they filled out the Demographics CRF.

11.1.2 Enrollment

A separate informed consent for the qualitative sub-study will be verbally obtained from participants at the time of the interview. An oral consent script will be used to provide details of the interview procedures to research participants including study risks and benefits, what would be required of the research participant, and alternatives to participation. The script is available in the Appendix. Potential research participants will be given time to ask questions and can reschedule the interview if they would like additional time to consider participation. Interested participants will be able to provide oral consent to participate. Oral consent will be documented by the study coordinator in the original interview recording. Oral, rather than written, consent is being used because some interviews will take place by telephone.

11.1.3 Interviews

Interviews will take place at a time chosen by the interviewee and can be conducted in person, via telephone call, or via virtual meeting, based on the participant's preference. Interviews will be audio recorded and transcribed verbatim with the exception that personal identifying information will be removed. Interviews will be semi-structured following our conceptual model of participant-centered recruitment and retention adapted from Chhatre et al. (see Appendix for interview guides).³⁰ Probing questions will provide depth and detail about how recruitment and retention strategies could be improved. Following analysis of the interview materials (see section 11.3.1 below), a synthesis of the findings will be emailed to interviewees to ensure that the descriptions are salient and credible. Emails will also offer an opportunity for feeding back preliminary data as a means of improving study retention. For participants completing a recruitment interview that declined enrollment in the care algorithm part of the study, the Demographics form will be completed at the end of the interview.

11.1.4 Remuneration

Interviewees will receive \$50, with an average interview lasting 30 minutes.

11.2 Recruitment and Retention Data Collection (Quantitative Data Collection)

We will use recruitment and retention data to assess the impact of the initial strategies and subsequent adaptations. We will keep logs of participant recruitment and retention. For healthcare worker (rural providers and schedulers) recruitment, we will record how many healthcare workers at each site: 1) were emailed an invitation to the recruitment meeting, 2) met with the study PI or research coordinator, and 3) consented to participate. Retention for healthcare workers will be defined as not having withdrawn consent to participate in the study and will not be based on their use of the integrated care model, since deviation from the model will be allowed if it is in the best interest of the patients as determined by the participating rural provider. Retention for administrators and other staff not formally consented in the quantitative portion will be defined as willingness of the clinic to continue to support the research endeavors.

For patient participant recruitment, we will record the number of patients who: 1) were contacted by phone, 2) completed the face-to-face appointment, and 3) consented to participate. For patient participant retention, we will log how many patient participants withdrew from the study or were lost to follow up before the 3-month telephone call. Logs will separate data into three distinct groups corresponding to adaptive iterations of the recruitment and retention strategies.

